15.2. Treatment Period (Weeks 3 to 6) /End of Study (Week 7)

						Treatmo	ent Perio	d					EOS
Visit Number	V11	V12	V13	V14	V15	V16	V17	V18	V19	V20	V21	V22 (EOT)	V23
Study Week	7	Week 3*			Week 4		,	Week 5*			Week 6	Ó	Week 7
Study Day(s) (± 1)	Day 15	Day 17	Day 20	Day 22	Day 24	Day 27	Day 29	Day 31	Day 34	Day 36	Day 38	Day 41	Day 43
Procedure													
Physical examination													X
12-lead ECG													X
Targeted physical examination	X	X	X	X	X	X	X	X	X	X	X	X	
Weight	X	X	X	X	X	X	X	X	X	X	X	X	X
Vital signs ¹	X	X	X	X	X	X	X	X	X	X	X	X	X
Laboratory tests ²		X	X		X	X	X	X	X	X	X	X	X
Column size			S-2	25					S-3	35			
Hemodialysis blood- flow rate (mL/min)		250		Ţ	Jp to 45	0		250		1	Up to 45	50	
Assessment of fluid status	X	X	X	X	X	X	X	X	X	X	X	X	
Kt/V assessment		X			X			X			X		
Adverse events and concomitant medications	X	X	X	X	X	X	X	X	X	X	X	X	X

^{*}The escalation to the subsequent column-size and flow-rate combination of the column will occur mid-week (e.g., on Wednesday for subjects on a Monday/Wednesday/Friday schedule and on Thursday for subjects on a Tuesday/Thursday/Saturday schedule).

^{1.} For additional information, see Section 7.1.1.2.2 Monitoring of Vital Signs.

^{2.} For additional information, see Section 15.3 Schedule of Laboratory Tests.

Protocol AKST1210-101 V2.1 13MAY2021

15.3. Schedule of Laboratory Tests

Assessment	Screening	I	Run-i	n									Treat	tment]	Period								End of Study (EOS)
	V1	V2	V3	V4	V5	V6	V7	V8	V9	V10	V11	V12	V13	V14	V15	V16	V17	V18	V19	V20	V21	V22 (EOT)	V23
b2M/proteomics				X			X			X			X			X			X			X	X
Serum pregnancy (WOCBP only)	X			X																			X
Hematology						Note	: CBC	, Hp, I	Hgb, aı	nd plasr	na-free l	Hgb sho	uld be ta	aken AI	TER H	D V4-V	21.						
Complete blood count (CBC)	X					X			X									X			X		
Haptoglobin (Hp)				X		X			X									X			X		
Hemoglobin (Hgb)	X					X			X									X			X		X
Plasma-free Hgb				X		X			X									X			X		
Chemistry			Note	: BUN	and (Creatin	ine sh	ould b	e colle	cted BE	FORE a	and AFT	ER HD										
Alanine aminotransferase (ALT)	X											X											
Albumin	X											X											
Aspartate transaminase (AST)	X											X											
Bicarbonate (HCO ₃)	X											X											
Bilirubin (total)	X											X											
Blood urea nitrogen (BUN)	X		X			X			X			X			X			X			X		
Calcium (Total)	X						X															X	
Chloride (Cl)	X											X											
Creatine kinase (CK)	X																						
Creatinine	X		X			X			X			X			X			X			X		
Glucose	X						X					X										X	
Hemoglobin A1c (HbA1c)	X																						

Protocol AKST1210-101 V2.1 13MAY2021

Assessment	Screening	I	Run-ii	n									Treat	ment l	Period								End of Study (EOS)
	V1	V2	V3	V4	V5	V6	V7	V8	V9	V10	V11	V12	V13	V14	V15	V16	V17	V18	V19	V20	V21	V22 (EOT)	V23
Lactate dehydrogenase (LDH)	X																					(= 0 = 7	
Magnesium (Mg)	X																						
Potassium (K)	X											X											
Phosphate	X											X											
Protein (total)	X											X											
Sodium (NA)	X											X											
Coagulation																							
Activated partial thromboplastic time (aPTT)	X											X											
Prothrombin time (PT/INR)	X											X											
Serology																							
Hepatitis B surface/core antigen (HBsAg)	X																						
Hepatitis C antibody (HCV Ab)	X																						
Human immunodeficienc y virus antibody (HIV Ab, HIV1/HIV-2)	X																						
Other Clinical Labs	Note: All la section should						Note	: All la	ıbs in 1	he "Otl	ner Clini	cal Labs	s" sectio	n shoul	d be col	lected E	BEFORE	E and A	FTER H	D at V7	and V2	.22.	
Adrenocorticotro pic hormone (ACTH)				X			X															X	
Complement (total)(CH50)				X			X															X	
Complement C3 and C4				X			X															X	
Complement C5a				X			X															X	
Gastrin				X			X															X	
Heparin Anti-Xa			X			X			X			X			X		X			X			X

Protocol AKST1210-101 V2.1 13MAY2021

Assessment	Screening	I	Run-i	n									Treat	tment]	Period								End of Study (EOS)
	V1	V2	V3	V4	V5	V6	V7	V8	V9	V10	V11	V12	V13	V14	V15	V16	V17	V18	V19	V20	V21	V22 (EOT)	V23
(only for patients on low molecular weight heparin)																							
Insulin				X			X															X	
Insulin-like growth factor- binding protein 1 (IGFBP1)				X			X															X	
Osteocalcin				X			X															X	
Parathyroid hormone (PTH)				X			X															X	
Terminal complement complex (sC5b-9)				X			X															X	
Thyroid- stimulating hormone (TSH)	X						X															X	

17. APPENDICES

17.1. Escalation, De-escalation, and Discontinuation Rules for Treatment with the Column

The purpose of the escalation rules is to ensure the safety of the subject when transitioning to a larger-size column. Since the main risk of — IDH — is related to column size, the occurrence of IDH will be the main criterion used to determine the appropriateness of escalation to a larger column size; however, other factors will be considered when escalating, including the overall status of the subject, other AEs, laboratory abnormalities, adequacy of HD, etc.

The following definitions are relevant to evaluating whether to escalate, de-escalate, or discontinue a subject:

- *Intradialytic hypotension/hypotensive (IDH) event*: An SBP < 90 mmHg confirmed by repeat measurement.
- **Expected IDH Rate**: The expected number of occurrences of IDH per weekly treatment period used to assess escalation, de-escalation, and discontinuation. Expected IDH Rate is derived from a subject's Historical IDH Rate (see table below).
- Historical IDH Rate: The number of occurrences of IDH as documented in a subject's medical record during a recent 8-week period prior to the run-in period. Subjects with 7 or more IDH events during this 8-week interval will be excluded.

Table 3 below provides the corresponding Expected IDH Rate based on the Historical IDH Rate and summarizes the rules for escalation, de-escalation, or discontinuation based on the number of occurrences of IDH.

Historical IDH Rate over 8 Weeks	Expected Weekly IDH Rate	Escalate to Next Column Size or Blood- Flow Rate if IDH Rate	De-escalation to Previous Treatment or Discontinue from

Table 3. Guidance for Escalation, De-escalation, and Discontinuation Based on IDH Rate

Historical IDH Rate over 8 Weeks	Expected Weekly IDH Rate	Escalate to Next Column Size or Blood- Flow Rate if IDH Rate in 1 Week is:	De-escalation to Previous Treatment or Discontinue from Study if IDH Rate in 1 Week is:
0	< 1	0	
1	< 1		
2	< 1	1 1	> 1
3	< 1	1 or less	
4	< 1		
5	< 1	2 or less	> 2
6	~1	Z or less	/ 2

17.1.1. **Escalation Rules**

A subject may be escalated to the next larger column size or next blood-flow rate if they experience no more than the number of IDH events described in Table 3, maintain an Hgb level \geq 9 g/dL, and have no other safety signals that the investigator believes could put the subject at risk. If a subject has an SBP < 90 mmHg, confirmed by repeat measurement, before the start of

HD, the subject will be withdrawn from the study because this constitutes significant hemodynamic compromise.

If a subject cannot attain the planned high blood-flow rate (450 mL/min) due to technical factors (e.g. differential pressures in the dialysis circuit), the investigator can adjust the blood-flow rate down to such a rate that allows the column to be tested at a higher rate than 250 mL/min.

[figure not shown]

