The duration of each HD treatment will be adjusted to ensure adequate Kt/V with a reduced flow rate (approximately 4-6 hours at 250 mL/min, 3-4 hours at up to 450 mL/min). During each week determination of HD adequacy will include KtV > 1.2 (calculated from measurements of blood urea) and urea reduction ratio (URR) (weekly URR > 65%).

The most important known potential risk for use of the column is an increased risk of IDH. Risk mitigations may include prophylactic administration of saline, supine positioning/lower limb elevation, avoidance of fasting before HD, avoidance of food intake during HD, use of cooled dialysate, education about the importance of avoiding excessive fluid gain between HD sessions (interdialytic weight gain), and avoiding the use of ultrafiltration rates (UFR) above 13 mL/kg/h. Concomitant medications, especially medications related to or affecting blood pressure (BP), should remain stable while on study and receiving HD with the

The occurrence of IDH events during each week, as outlined in Appendix 17.1: Escalation, De-escalation, and Discontinuation Rules for Treatment with the Column, will be one factor used to determine column size/blood-flow rate escalation/de-escalation as well as discontinuation from the study. There is also a possibility that the blood-flow rate of 450 mL/min cannot be attained due to factors related to the dialysis circuit or other technical issues. If the blood-flow rate of 450 mL/min cannot be attained, it can be adjusted down to enable continued dialysis at a blood-flow rate as high as possible. The reason(s) for the inability to attain a blood-flow rate of 450 mL/min must be documented.

Endpoints:

Primary Endpoints:

- Safety and tolerability of each column size at each blood-flow rate.
 - Evaluation of safety and tolerability will include assessment of the rate and severity of all adverse events (AEs), with analyses of adverse device effects (ADEs), treatment-emergent AEs (TEAEs), number of IDH events, and changes in total and free hemoglobin (Hgb).
 - Tolerability will be assessed by the proportion of subjects who can escalate to and tolerate each column size and blood-flow-rate combination.

Secondary Endpoints

- Weekly Kt/V and URR.
- Total fluid balance for each column-size flow-rate combination.
- Proportion of subjects who are able to achieve the dry weight goal during the allotted HD duration for each column size and flow rate combination.

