4. STUDY DESIGN AND ENDPOINTS

4.1. Description of the Study Design

This is an open-label study in subjects between 40 and 75 years of age who have ESRD requiring HD. Assuming a drop-out rate (unrelated to safety and tolerability) of 20%, approximately 15 subjects will be enrolled to obtain 12 evaluable subjects. The column will be connected in series before (upstream) of the dialysis cartridge for the duration of each HD session. Only single-use dialyzers will be used during the study.

After screening (Visit 1), subjects will undergo HD at a lower blood-flow rate (250 mL/min) for a 1-week run-in period to determine the HD duration required to achieve adequate Kt/V (> 1.2). Daugirdas' formula will be used to calculate Kt/V (Daugirdas 1993, Daugirdas 1995, Daugirdas and Schneditz 1995).

The column size will be increased from S-15 (150 mL) to S-25 (250 mL) to S-35 (350 mL), as tolerated, and blood-flow rates will be evaluated at 250 mL/min and up to 450 mL/min as tolerated (see Appendix 17.1: Escalation, De-escalation, and Discontinuation Rules for Treatment with the Column). Each column-size and blood-flow rate combination will be evaluated during 3 consecutive HD sessions (1 week) before proceeding with the next combination, as follows (and as shown in the Schematic of Study Design):

The first treatment with the column S-15 (150 mL) will occur mid-week (e.g., on Wednesday for subjects on a Monday/Wednesday/Friday schedule and on Thursday for subjects on a Tuesday/Thursday/Saturday schedule).

The escalation to the subsequent column-size and flow-rate combination will occur mid-week (e.g., on Wednesday for subjects on a Monday/Wednesday/Friday schedule and on Thursday for subjects on a Tuesday/Thursday/Saturday schedule).

The duration of HD time will be adjusted for flow rate (approximately 4-6 hours for 250 mL/min, 3-4 hours for up to 450 mL/min). During each HD session, measurements of HD effectiveness will include Kt/V > 1.2 (calculated from measurements of blood urea) and URR (weekly URR > 65%).

The incidence of IDH events, as defined in Appendix 17.1: Escalation, De-escalation, and Discontinuation Rules for Treatment with the Column, will be one factor used to determine column size/blood-flow rate escalation/de-escalation as well as discontinuation from the study.

The planned duration of subject participation is approximately 12 weeks (up to 4 weeks for screening and 8 weeks on-study, which is inclusive of the 1-week run-in period).

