10.5. Sample Size

The sample size for this study was based on FDA Guidance for the Content for Premarket Notifications for Conventional and High Permeability Hemodialyzers (FDA 1998) which recommends that data be collected for a minimum of 12 subjects for a minimum of 36 treatments. In this study, approximately 15 subjects between 40 and 75 years of age with ESRD will be enrolled. Assuming a drop-out rate of 20% (unrelated to safety) enrollment will yield approximately 12 evaluable subjects. With regard to the most important risk of IDH, a sample of 12 subjects will provide approximately 70% probability of detecting at least 1 IDH event in each week (i.e., for each column size and blood-flow rate combination). This estimate is based on the assumption that the rate of IDH in the general ESRD population, using the Nadir 90 definition, is 10%, based on a study in over 10,000 US patients undergoing HD (Flythe 2015).

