4.2.2 Evaluable Population

The Evaluable population will consist of all subjects who completed blood-flow rates up to 450 mL/min for at least 1 column size (e.g., S-15 at 250 and up to 450 mL/min).

4.2.3 b2M Population

The b2M Population will consist of a subset of the evaluable population that excludes any subjects with Major Protocol Deviations pertaining to blood flow rate as well as any subjects who have documented blood flow rate deviations exceeding +/- 20 mL/min of the protocol-specified blood flow rate at Visits 4, 7, 10, 13, 16, 19 and/or 22.

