4.7.4 Tolerability of each Column Size and Blood-flow-rate Combination

The number and percentage of subjects will be summarized for the Safety, Evaluable and PP populations, by each column size and blood-flow rate combination and total for the following:

- Subjects entered each column size/blood-flowrate combination
- Subjects who de-escalated to a lower column size categorized by reason: IDH, anemia, or other. Anemia (as it pertains to de-escalation) is defined as having an Hgb lab value of < 9 g/dL despite receiving optimized treatment with erythropoietin stimulating agents (ESA).
- Subjects who were discontinued due to safety, tolerability, and/or investigator discretion
- Subjects who completed all the visits

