4.8.1 Hemodialysis Parameters

Kt/V and URR (%) will be summarized for the Safety, Evaluable and PP populations, by visit and each column size/flow-rate combination.

Kt/V will be calculated with Daugirdas' formula from the pre-dialysis to post-dialysis urea nitrogen ratio (R), the weight loss (UF), session length in hours (t), and anthropometric or modeled volume (V) using the equation: $Kt/V = In (R - 0.008 \times t) + (4 - 3.5 \times R) \times 0.55 \text{ UF/V}$ (Daugirdas 1995).

URR (%) is calculated as:

URR (%) = (1 - post-dialysis BUN / pre-dialysis BUN) * 100

For evaluation of total fluid balance, the initial fluid removal goal (mL), actual fluid removal (mL), and amount differs from the goal will be summarized by column size and blood-flow rate combination.

Actual fluid removal is calculated as follows: Weight (kg) – Weight Post-Dialysis (kg) and subsequently converting weight to volume (1 kg = 1000 mL).

In addition, the number and percent of subjects who achieved the dry weight goal (i.e., Weight Post-Dialysis (kg) is less than or equal to Estimated Dry Weight) will be summarized by column size and blood-flow rate combination.

A listing of HD parameters will be provided. Other HD parameters will not be summarized but will be provided in the listing only.

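### High-flow tolerability is counted by nominal flow and achieved flow is only listed, so the tables cannot show how far the 250 versus up-to-450 mL/min contrast was delivered

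*Protocol*

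**What the plan says.** **What the high-flow week may be.** Protocol 17.1.1 covers the case where 450 mL/min is not attained because of technical factors, such as pressures in the dialysis circuit. The investigator "can adjust the blood-flow rate down to such a rate that allows the" column to be tested above 250 mL/min. The Protocol Summary words the allowance differently: "it can be adjusted down to enable continued dialysis at a blood-flow rate as high as possible". It also requires the reasons to be documented.

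**How tolerability is counted.** The primary tolerability endpoint (Protocol 4.2.1, SAP 2.3) is the proportion of subjects who can escalate to and tolerate each combination. SAP 4.7.4 implements it with four counts: "Subjects entered each column size/blood-flowrate combination", those de-escalated by reason, those discontinued, and those completing all visits. The Evaluable definition (Protocol 10.3, SAP 4.2.2) requires completion of the up-to-450 condition for at least one column size. No minimum flow appears in either place.

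**What happens to achieved flow.** Protocol 7.1.1.1.6 captures mean and maximum flow, and reasons for changes in flow, at every session. SAP 3.1 names the CRF from which mean and maximum flow are derived. SAP 4.8.1 specifies summaries of Kt/V, URR, fluid balance and dry-weight attainment, and then states: "Other HD parameters will not be summarized but will be provided in the listing only".

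**The one numeric flow criterion.** SAP 4.2.3 excludes from the b2M Population subjects with "documented blood flow rate deviations exceeding +/- 20 mL/min of the protocol-specified blood flow rate" at seven named visits.

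**The concern.** The study compares two blood-flow rates within each column size, and both documents say the effect of flow will be assessed for a given column size. That comparison is only as informative as the separation in flow actually delivered. A week run at 450 and a week run somewhat above 250 fall under the same heading in every planned table of safety and tolerability.

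A reader of the primary tolerability table would see a proportion completing S-35 at up to 450 mL/min and would naturally read it as evidence about flows near 450. Nothing in the specified tables would confirm or qualify that reading. It would have to be reconstructed from a listing, using a cut-off chosen after the data were seen. The similarity or difference in adverse events and IDH between the two flow conditions would be equally hard to interpret if the delivered separation were unknown.

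**Working it through.** **1. The plan's own figures.** Protocol 10.5: "Assuming a drop-out rate of 20% (unrelated to safety) enrollment will yield approximately 12 evaluable subjects". This reproduces: 12 / (1 − 0.20) = 15. The stated chance of about 70% of seeing at least one IDH event in each combination also reproduces, taking the assumed 10% as a rate per subject per week: 1 − 0.9^12 = 0.718. The point below is about definition and reporting and does not challenge either figure.

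**2. The range the rule permits.** The nominal ratio is 450 / 250 = 1.8 and the nominal step is 450 − 250 = 200 mL/min. The share of the step delivered at flow f is (f − 250) / 200:

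- 251 mL/min: 1 / 200 = 0.5%
- 300 mL/min: 50 / 200 = 25%
- 350 mL/min: 100 / 200 = 50%
- 450 mL/min: 200 / 200 = 100%

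If such a rate were the highest attainable for technical reasons, each would be tabulated as up to 450.

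**3. What a complete table could conceal.** The documents give no shortfall rate, so the number m of 12 subjects running near 450 is an assumed range. Suppose all 12 complete the nominal up-to-450 week. The planned table reports 12/12 = 100% (exact 95% CI 73.5% to 100%) in every row below. Intervals are Clopper-Pearson, in line with the exact methods named in Protocol 10.1. The last column is 1 − 0.9^m, keeping the protocol's 10% rate.

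| m near 450 | Proportion tolerating near-450 flow (exact 95% CI) | Chance of at least 1 IDH event near 450 |
|---|---|---|
| 12 | 100% (73.5% to 100%) | 71.8% |
| 10 | 83.3% (51.6% to 97.9%) | 65.1% |
| 8 | 66.7% (34.9% to 90.1%) | 57.0% |
| 6 | 50.0% (21.1% to 78.9%) | 46.9% |
| 3 | 25.0% (5.5% to 57.2%) | 27.1% |

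**4. Effect on the contrast.** Again by assumption, take 8 subjects at 450 and 4 at 300: (8 × 450 + 4 × 300) / 12 = 400 mL/min. The delivered contrast is then 400 − 250 = 150 rather than 200 mL/min.

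**5. Whether another planned output closes the gap.**

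- SAP 4.10 promises adherence tables for each column size and flow rate but names no flow metric.
- SAP 4.5 tabulates protocol deviations by combination, but a reduction the protocol permits is not clearly a deviation. For the same reason, the Per-Protocol summary does not reliably separate these subjects.
- SAP 4.9.3 defines a listing that can flag flow changes close to a low SBP. It is not a table and does not cover technical reductions.
- SAP 4.2.3 applies its tolerance to b2M only.

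None of these specifies a summary of achieved flow.

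**The case against.** The strongest defence is that the plan is accurate as written. The objective is tolerability at flows greater than 250 mL/min, the column heading says up to 450, and a completer at a lower attained rate satisfies both. The reduction is not a free choice: it applies to technical limits, the Summary asks for the highest possible rate, and the reason must be recorded. Subjects must habitually dialyse at 400 to 500 mL/min (inclusion 5), and those not expected to tolerate 450 are excluded (exclusion 6). The study is small and descriptive, and about 36 session rows per combination (12 × 3) can be read from a listing. The table shells are separate attachments and might add something.

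Most of this stands, and it limits the point. Large shortfalls are less likely, though the usual flows in the entry criteria are achieved without the column in the circuit, and the protocol itself provides for failure to reach 450. A listing does not qualify a headline proportion, and the SAP text says listing only.

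Four stronger readings are tempting but not supported:

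- *The primary result is biased upward.* This presupposes a target quantity at 450 mL/min, which neither document defines.
- *The SAP contradicts itself, because a session at 380 mL/min could be a deviation in 4.2.3 and a completed high-flow session in 4.7.4.* The 20 mL/min tolerance restricts a separate population for a secondary analysis. A narrower set there does not conflict with the tolerability counts.
- *SAP 4.9.3 expects flow to be changed when SBP falls below 90.* It only defines which records enter a listing.
- *Failure to reach about 430 mL/min should count as intolerance in the primary row.* That would classify circuit limits as intolerance, which the protocol treats as technical.

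**Conclusion.** The concern holds as a reporting gap. With no numeric floor beyond staying above 250 mL/min, counting by nominal combination and achieved flow left to a listing, the specified tables cannot show how far the flow contrast was delivered or what flow was tolerated. The label remains literally true.

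The size cannot be stated from the documents. At the extreme the rule lets the ratio fall from 1.8 to just above 1.0; the entry criteria make that unlikely. The figures for 3 to 10 of 12 subjects near 450 are assumptions that show what a reported 100% could conceal, not forecasts. The IDH column also assumes that the 10% rate does not depend on flow. The change is worth making before analysis because it affects what can be concluded about the comparison at the centre of the study.

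**What to change.** **SAP 4.8.1.** Summarise achieved mean and maximum blood flow (n, median, minimum, maximum) by column-size and flow combination, replacing listing-only reporting for these variables. Tabulate the documented reasons for flow reduction as technical versus hypotension or other clinical.

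**SAP 4.7.4.** Keep the current rows. Add a supportive breakdown of those completing each up-to-450 combination by a pre-stated achieved-flow category: for example, within the SAP's own 20 mL/min tolerance of 450 (450 − 20 = 430 or above) versus lower. Show technical shortfall separately and do not count it as intolerance. This is a reporting category, not a rule for conduct.

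**Conclusion.** State the high-flow tolerability result in terms of the flow achieved.

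**Protocol.** The Summary and 17.1.1 describe the permitted reduction differently (as high as possible; above 250 mL/min). The sponsor should reconcile them. No flow rule is proposed here.

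**Cost.** SAP wording and one or two tables from data already captured. The downside is that the high-flow tolerability statement may look less favourable.
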